If the treatment is statistically significant in the appropriate direction, we will conduct exploratory treatment modification analyses (i.e., treatment heterogeneity), of the interaction term of β_5 (fixed portion) and $\beta_6 t$ (random portion). Again, we will base our interpretations on clinical meaningfulness of the effect size estimates and CI's. We will also test if the treatment effect varies by the CR's diagnosis, CG sociodemographics (e.g., CG gender, age, ethnicity), CG job type (flexible vs. inflexible) and CG occupational factors. We will conduct an exploratory dose-response analysis within the SOS care group. Finally, to further guide the interpretation of study results across subgroups of intervention participants and support future implementation efforts, we will also compare summaries derived from the rapid qualitative content analyses.

10. Withdrawal of Subjects

10.1. Describe any anticipated circumstances under which subjects will be withdrawn from the research without their consent.

N/A

10.2. Describe the consequences of a subject's decision to withdraw from the research and the procedures for orderly termination of participation by the subject (e.g., the subject contacting the investigator for an end-of-study visit).

Participants will be made aware that they may withdraw from this study at any time during the course of the research/care management assessments/visits without penalty or loss of VA or other benefits to which they are entitled. If a patient chooses to withdraw from the study, a note will be made in their study file. Since the caregivers are the participants, they are the ones who can request to withdraw from the study.

11. Reporting

11.1. Include procedures for reporting unanticipated problems, serious adverse events, and protocol deviations.

All protocol deviations, breaches of confidentiality, adverse events or other problems will be identified and reported to the local site's IRB, Privacy Officer, and/or Information Security Officer after discovery, as stipulated by regulations. All breaches of confidentiality will be immediately (within 1 hour) reported to the ISO and Privacy Officer. Non-serious adverse events and anticipated adverse events and problems will be logged and discussed in the routine supervision of research staff. The PI will initiate review of concerns arising from the ongoing review of non-serious and anticipated adverse events that appear to impact the study/risk ratio on an ad hoc basis. All serious adverse events and non-serious unexpected events will be reported to the PI and IRB in accordance with Good Clinical Practice Guidelines and IRB Regulations. Severe adverse events (SAEs) (e.g., hospitalization, death), will be reported to the PI within 24 hours and to the IRB within 48 hours. Unexpected adverse events will be reported to the IRB within 72 hours. Minor and anticipated adverse events and problems will be logged and reported in the annual/continuing review to the IRB.

The Principal Investigator will be responsible for reviewing any adverse events or issues with the protection of subjects. Should there be a need for a clinical intervention, one of the clinicians on the study ([name], [name], [name], or [name]) will provide said intervention.

12. Privacy and Confidentiality

12.1. Describe whether the study will use or disclose subjects' Protected Health Information (PHI).

Veteran/CG PHI and identifiers (e.g., first, middle, last names; SSN's; addresses and phone numbers; date of birth; age over 90 years; ID numbers/medical record numbers; and dates/procedural codes associated with health service utilization and pharmacy records) extracted from CPRS or VINCI will remain in the designated study folder on the MIRECC or VINCI secure servers. PHI will primarily be used for recruitment and tracking purposes. PHI will not be disclosed.

12.2. Describe the steps that will be taken to secure the data (e.g., training, authorization of access, password protection, encryption, physical controls, Certificates of Confidentiality, and separation of identifiers and data)

Procedures for protecting against or minimizing potential risks to participants' privacy or confidentiality over the course of data collection, storage, management, and analysis will be guided by our past work with similar research methods and participants as those proposed here. Procedures include: 1. formal training sessions for all research staff emphasizing the importance of confidentiality; 2. specific procedures developed to protect CRs'/CGs' confidentiality, and 3. formal mechanisms limiting access to information that can link data to individual respondents.

During collection of research assessment data and care management calls we will ask CGs whether they are in a private, comfortable setting and if they are assured that their responses are

not being monitored by another person. The data collection records and any collected PHI will remain confidential. Upon providing informed consent CGs will be assigned a random Study ID number/code, absent of any personal or identifying information. Hence, all research and clinical data used in analyses will be coded. In order to ensure participant privacy and confidentiality, this Study ID number will be used on all electronic research datasets, and in cases where CGs prefer to complete the research assessments at home, on data collection forms. All coded electronic dataset(s) will be located on a shared VA folder created on the MIRECC's secure, password-protected server. Any hard copies of records that contain direct subject identifiers (e.g., name, assessment dates) will be stored in a separate locked filing cabinet in the CM's office. Moreover, forms with identifiable information will be kept separate from de-identified data forms, which will only be labeled with the participants' Study IDs. Only the PI and research staff will have access to these files, except in the case where the VA IRB and other federal regulatory agencies request access for auditing purposes.

To further ensure Veterans' and CGs' privacy, the clinical databases that include Veteran/CG PHI and identifiers (e.g., first, middle, last names; SSN's; addresses and phone numbers; date of birth; age over 90 years; ID numbers/medical record numbers; and dates/procedural codes associated with health service utilization and pharmacy records) extracted from CPRS or VINCI will remain in the designated study folder on the VINCI or MIRECC secure servers. However, at the point of conducting analyses, a separate research database will be created, de-identified of any personal or identifying information (i.e., all fields with PHI or identifiers will be removed), and kept in a separate password protected file on the shared VA folder created on the MIRECC server. We will merge this file with the self-report research and CM assessment data. To protect confidentiality during the course of coding, cleaning, and analyzing data, we will use these de-identified, merged research databases. The PI and Biostatistician will be responsible for analyzing the data, and all data entry and analysis will take place on the MIRECC server using the coded databases. To facilitate data tracking and monitoring, the PI and her designee will maintain, under a limited password, a lookup database that links the research database to the original clinical databases with PHI in the event that identification of the individual Veteran is necessary. The lookup database linking the study IDs and PHI will be kept on the designated study folder on the VINCI or MIRECC server and routinely monitored by the PI.

Should there be any breaches of confidentiality, improper use or disclosure, or deviations to the protocol during this process, the PI will report these incidents to the IRB, Associate Chief of Staff for Research, and Research Compliance Officer at the local site. All breaches of confidentiality will be immediately reported to the Information Security Officer and Privacy Officer. PHI extracted for the purposes of this project will under no circumstances leave the CMCVAMC or VINCI servers. In order to protect participants' privacy and confidentiality, we will follow the Health Insurance Portability and Accountability Act of 1996 and its privacy regulations and all other applicable laws when handling participants' data.

13. Communication Plan for Multi-Site Studies or Studies being done at Non-CMCVAMC Locations

N/A; skip to question 14

13.1. Include plan for ensuring all required local site approvals are obtained and notifying the Director of any facility where the research is being conducted but the facility is not engaged.

This is a two-site study. We have conducted intervention trials in collaboration with the VA NYHHS CIH before (including a current two-site caregiver study). During weekly meetings, staff will discuss any IRB-related activities (approvals, modifications, reporting etc.) and discuss recruitment and enrollment numbers.

13.2. Include plan for keeping all engaged sites informed of changes to the protocol, informed consent, and HIPAA authorization.

We will discuss any changes to the protocol, IC, and HIPAA procedures during weekly meetings, and have all IRB documents shared on a shared VA server. This has been effective in managing and tracking procedures and changes across our two sites in past trials.

13.3. Include plan for informing local sites of any Serious Adverse Events, Unanticipated Problems, or interim results that may impact conduct of the study.

All serious adverse events and non-serious unexpected events will be reported to the PI and IRB in accordance with Good Clinical Practice Guidelines and IRB Regulations. Severe adverse events (SAEs) (e.g., hospitalization, death), will be reported to the PI within 24 hours and to the IRB within 48 hours. Unexpected adverse events will be reported to the IRB within 72 hours. Minor and anticipated adverse events and problems will be logged and reported in the annual/continuing review to the IRB.

13.4. Include plan for ensuring the study is conducted according to the IRB-approved protocol.

The PI and Research Coordinator will routinely evaluate and assess data quality and adherence to the IRB-approved protocol. Updates and issues will be discussed during weekly team meetings.

13.5. Include plan for notifying all local facility directors and LSIs when a multi-site study reaches the point that it no longer requires engagement of the local facility (e.g., all subsequent follow-up of subjects will be performed by the PI from another facility).

We will discuss updates and enrollment numbers during weekly calls.

14. References (bibliography of cited literature)

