B.1 Screening, Baseline and 4 and 9 month Follow-up Research Assessment Procedures: Once the CG is identified (by self-referral, VA providers, or VINCI), indicates an interest in study participation, and consents (in-person or by phone), the RA will complete the initial screening and, if the CG is eligible, the baseline research assessment. Next, to ensure blinding of the RAs, the Project Coordinator will use a random number table to inform each CG of their group assignment. Procedures for the assigned study arm will commence (see B.2 and B.3). All CGs will be contacted again for 4- and 9-month follow-ups, at which point the majority of baseline assessments will be re-administered. Before each assessment, RAs will remind CGs not to disclose their assigned study arm. Data on care recipients' (CRs') health and service utilization will be extracted from the CRs' clinical record via VINCI, while CG VA and non-VA CG/CR health

and service utilization will be captured by CG assessment. All research assessments (including follow-ups) will be completed by the RA by telephone (with an email/mail-in option, if preferred) and include validated questionnaires regarding CR- and CG-level sociodemographic, clinical, work- related, and psychosocial variables (Appendix 1; Table 1). In-depth qualitative interviews will be conducted at 4-month follow-up with a subgroup of CGs (n=30) from the SOS arm.

These qualitative interviews will be audio recorded.

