As part of SOS care, the CM will administer and document results from a brief C-WLQ every other session. For purposes of tracking the care process, the CM will document each contact with CGs, referrals to VA/community service agencies, and each contact with Veterans' PCPs/providers (when indicated) and results. Finally, in cases where CGs report needing assistance with the Veterans' care, CMs will track whether concerns were discussed with the Veterans' PCPs and whether recommendations were made or help was coordinated for scheduling in primary and specialty care.

To complement the quantitative data analyses, we will use rapid qualitative content analysis to evaluate the intervention's acceptability, appropriateness, and value of the content from the CGs' perspective. Rapid qualitative content analysis is a “telescoped”, action-oriented approach to consolidating and summarizing qualitative data.⁷⁷ At the end of the first follow-up research visit (i.e., 4 months), 30 CGs will be purposively sampled on characteristics that can inform interpretation of results and future implementation efforts (i.e., CR condition, age) and asked semi-structured questions (e.g., which outcomes do they value most/least, positive/negative program experiences, what components they found most helpful, what they would change about the program, etc.) (see Appendix 3). After each interview (which will be conducted by the Research Coordinator), we will create a structured, summative memo (organized into summary matrices) that documents responses to a predetermined set of domains (e.g. positive/negative experiences, helpful components, recommendations, perceived value). Based on prior experience, each interview will take approximately 1 hour to review and summarize. Summaries will be compared across groups by Drs. [name] and [name], each of whom has experience with the use of qualitative methods and analyses in clinical trials.

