CMs also will enter clinical data into VA REDCap and the Behavioral Health Laboratory (BHL) software. The BHL software is a VA approved and network-wide installed software package that allows providers to track participants and to graphically display assessment reports. The software has been in use for more than 10 years in the VA. All REDCap and BHL data collection, transfer, and storage of data will be performed on the VA Intranet and thus access to the system is user based and requires maintenance of all relevant employee trainings. CR and CG- related VA and non-VA healthcare and service utilization will be obtained using VINCI or by self- report. When estimating non-VA utilization of care, we plan to follow HERC's guidebook which provides detailed documentation and suggestions for analyzing non-VA data on procedures.⁶⁸ The utilization database will include a "time window" variable spanning one year prior to and one year following the final CM call. Extracting clinical patient record data electronically to the greatest extent possible will improve validity and reduce respondent burden. Detailed procedures will be followed to protect against potential risks to privacy and breaches of confidentiality.

9. Data Analysis

9.1. Provide sample size determination and analysis (include anticipated rate of screen failures, study discontinuations, lost to follow-up etc.).

Power calculations were computed for Aim 1 based on 300 consenting CGs. Estimating a maximum of 20% attrition from follow-up (final n=120/group), typical correlation of .70 between baseline and each of two follow-ups, 5% significance tests, and 80% power, we will be able to find a minimum detectable effect size (MDES) of 0.235 standard deviations (SD). This is within the range of effect sizes found in other CG intervention studies.³⁷ For the primary outcome (Aim 1a) we expect a standard deviation for the K10 of about 10,⁵⁸ suggesting that we could detect a difference of 2.35 points between treatment and control based on mixed effects models. A clinically meaningful treatment-control difference of 3 points is well within the range of detectable differences. Similarly, for the secondary outcome measure (Aim 1b), a C-WLQ summary score improvement of lost productivity due to caregiving burden (SD=4.4%), will yield a MDES of 1.0%. Exploratory analyses will be underpowered.

9.2. Describe how, where and by whom the data will be analyzed.

All analyses will be run by the PI or Biostatistician.

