To yield findings that will be used to inform future research and implementation endeavors, we will run exploratory analyses (using the analytic strategy outlined above) that address Aim 2. Overall CG physical and mental well-being and CR utilization of VA and non-VA services (including CG-related services), will be modeled as dependent variables. Given that we are underpowered for a full-scale quality of care analysis, we will compare summary statistics and estimates (with confidence intervals) across groups for descriptive purposes as opposed to formal statistical hypothesis testing. We will model group differences in CR service use (using negative binomial models and chi-squares) using count data of utilization/appointments from VINCI and CG self-report surveys (which will ask about CR non-VA healthcare use and CG use of VA/non-VA support services). Service utilization will be operationalized as the number (simple count) and occurrence of any (yes/no) outpatient visits and inpatient admissions/hospitalizations, and the total number of days hospitalized/bed days. Outpatient visits will be further classified based on the visit stop code into medical or surgical, psychiatric/substance use, social work, occupational therapy, other specialty care, and ER encounters. Inpatient hospitalizations will be further classified based on the primary diagnosis for admission into medical or psychiatric/substance use hospitalizations. For each participant, all utilization data will be summed and compared over two intervals (1 year pre-baseline and 1 year post-4 month assessment). Inpatient and outpatient utilization will be analyzed separately. We will also carefully examine specific domains of utilization where we expect to see an effect, such as MH, social work, and occupational health visits. While the differences may not be statistically significant, even clinically meaningful increases in service use by the Veteran and CG would be consistent with the VA mission of improving access to care.

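### RA blinding for the K10 and C-WLQ is at risk and weakly protected: follow-up collects cues to arm, and the only safeguard stated there is a reminder to caregivers

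*Combined protocol and SAP*

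**What the plan says.** Section 16, 4.3.1, B.1 commits to blinded assessors: "to ensure blinding of the RAs, the Project Coordinator will use a random number table to inform each CG of their group assignment". For the follow-up calls, the stated safeguard is "Before each assessment, RAs will remind CGs not to disclose their assigned study arm".

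Three other parts of the plan bear on that commitment.

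- **Mode.** B.1 has RAs do the assessments by telephone, with mail or email as an option. Section 16, 8.1 adds Qualtrics, but expects RA telephone interviews to supply most of the data.
- **Service use.** B.1 says that caregivers' VA and non-VA health "and service utilization will be captured by CG assessment". Section 16, 9.2 describes the caregiver surveys as ones "which will ask about CR non-VA healthcare use and CG use of VA/non-VA support services".
- **Qualitative interviews.** B.1: "In-depth qualitative interviews will be conducted at 4-month follow-up with a subgroup of CGs (n=30) from the SOS arm". Section 16, 8.1 gives the timing: "At the end of the first follow-up research visit (i.e., 4 months), 30 CGs will be purposively sampled". The same paragraph assigns these interviews to the Research Coordinator. Sections 9 (item 2.3) and 16 (5.6) raise the 4-month payment from $25 to $35 for those who take part.

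Item order and exact wording belong to Appendix 1, Table 1, which is not in the copy reviewed.

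**The concern.** SOS is six one-hour sessions with a VA care manager over 3-4 months (B.2); usual care has one care manager call (B.3). A caregiver who has just been asked not to mention the arm may then be asked which VA support services they have used. An honest answer could describe the intervention. Hypothesis 2b itself predicts more use of needed services in the SOS arm, caregiver-related services included, so the plan expects these answers to differ by arm.

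The qualitative interview is a second cue: only SOS caregivers are eligible, and it follows the RA's 4-month visit. An RA who learns of it knows that caregiver's arm and may make the 9-month call.

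An RA who knows or suspects the arm can influence self-reports through prompting, tone and clarification. K10 and C-WLQ carry Hypotheses 1a and 1b, so the stake is interviewer bias in the main comparison. A trial report would also claim assessor blinding on the strength of a reminder alone.

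**Working it through.** **1. The plan's own scale.** Section 16, 9.1 gives 300 caregivers, 20% attrition (120 per arm), a correlation of 0.70, 5% tests, 80% power, and a detectable effect of 0.235 SD, or 2.35 K10 points at SD 10. I assume two-sided tests and a correlation of 0.70 between the two follow-ups as well. For a mixed model with 150 baselines and 120 followed per arm:

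- Residual variance of the two-visit mean given baseline: (1 + 0.7)/2 − 0.7² = 0.36.
- Per-arm variance: 0.36/120 + (1 − 0.7)²/150 = 0.0030 + 0.0006 = 0.0036.
- Standard error of the difference: √(2 × 0.0036) = 0.0849 SD, or 0.849 K10 points.
- Detectable effect: (1.960 + 0.842) × 0.0849 = 0.238 SD; power at 0.235 is 79.1%.

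The stated figure reproduces closely and is not in dispute. It serves only as a yardstick.

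**2. What each cue can tell the RA, and when.**

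- *Service-use answers.* They arise inside the caregiver assessment. Whether they come before K10 and C-WLQ in the same call cannot be checked without Appendix 1. Even if they come last, answers heard at month 4 precede the month-9 K10. Section 11, item 5 lists two RAs, so the same person could make both calls.
- *Qualitative interview.* It comes after the month-4 outcomes, so it can matter only at month 9, and only if the RA learns of it. The text does not say who selects or schedules these caregivers, or that the RA is kept unaware.

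**3. Reach of the qualitative route.**

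- By person: 30/150 = 20% of those randomized to SOS; 30/120 = 25% of those expected to be retained.
- By assessment: one affected call each, against 2 × 120 = 240 SOS follow-ups, is 30/240 = 12.5%. This is the relevant share for β3, which pools both follow-ups (9.2).

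**4. What a bias might look like.** The documents give neither an unblinding rate nor an interviewer effect. These figures are illustrations under assumed inputs, in which only SOS scores move.

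- Qualitative route, with an assumed shift of 1 to 3 K10 points per affected call: 0.125 × 1 = 0.125 to 0.125 × 3 = 0.375 points, which is 5% to 16% of 2.35.
- Service-use route, with an assumed 25% to 100% of SOS assessments unblinded and a shift of 0.5 to 2 points: 0.25 × 0.5 = 0.125 to 1.0 × 2 = 2.0 points. With no true effect, a two-sided 5% test would then reject 5.2% to 65% of the time. For example, 50% unblinded and a 1-point shift gives 0.5 points; 0.5/0.849 = 0.589 standard errors; rejection 9.1%.

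The width of the second range shows how little the documents fix the answer.

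**The case against.** A reader might infer that the follow-up interview discloses the arm and that RA blinding cannot hold. The documents do not support that.

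- VA support contact is expected in both arms. Usual-care caregivers get a care manager call, Caregiver Support Program material and encouragement to seek VA services; SOS caregivers are offered similar information (B.3). No supplied item names SOS or counts sessions. This stands: the answers are a cue, not disclosure.
- Appendix 1 may already put K10 and C-WLQ first, and the text does not tie the service-use items to particular visits. This stands as a limit on what can be checked. It does not remove the carry-over from month 4 to month 9 if the items are asked at month 4.
- The coordinator, not the RA, conducts the qualitative interviews, and payment is electronic. This stands. What is missing is any statement that selection and scheduling are kept from the RA.
- Caregivers know their own arm and may self-complete. True, so RA blinding guards only against interviewer influence. But that is the protection the plan claims, and it expects most data to come through RAs.

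A reader might also infer leakage through shared software, since "CMs also will enter clinical data into VA REDCap", which RAs also use. That rests on silence: Sections 11 (item 7.1) and 16 (8.1) describe individual log-ins and user-based access, and nothing says RAs can open care manager forms.

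Separately, Section 16, 3.1 lets the Research Coordinator, who may assign the arm, and where appropriate the Care Manager conduct research assessments. That conflicts more directly with B.1. It needs its own reconciliation, and resolving it would not close the routes described here.

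**Conclusion.** The concern holds in a limited form. B.1 promises RA blinding, the supplied text states only a reminder to protect it at follow-up, and the plan places two cues to arm in or next to the same contacts. Blinding is at risk and weakly protected; it is not shown to fail.

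The qualitative route is bounded at 12.5% of SOS follow-up assessments, given the plan's 20% attrition, and touches month 9 only. The reach of the service-use route is unknown because it depends on item wording and order in Appendix 1. No bias estimate follows from the documents, and no sample-size figure changes. The case for acting is that the change is nearly free and covers the primary and secondary outcomes.

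**What to change.** Amend B.1 and Appendix 1.

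1. At 4 and 9 months, complete and lock K10 and then C-WLQ before any other item, unless Appendix 1 already requires it.
2. Put service-use items last and word them to exclude contacts with the study care manager, which the care manager already logs (C.1). Alternatively, collect them by mail or Qualtrics, or through the coordinator. Order alone does not shield month 9 from answers heard at month 4, so where feasible have the other of the two RAs make the month-9 call.
3. Have the coordinator select, schedule and pay for the qualitative interviews in a separate contact after the RA has closed the 4-month visit, without telling the RA.

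Optional: confirm that REDCap rights keep care manager forms from RAs, and have the RA record a guess of arm once C-WLQ is locked, reported by arm.

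Cost: one extra contact for 30 caregivers and minor questionnaire reordering. Self-completed service-use items may come back less completely, but they feed exploratory outcomes only. The sample size, endpoints and assessment time points stay as they are.
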